We will layer data collection and the implementation of the combined-care model and social media campaign over three phases. Phase 1 is the pre-intervention phase and it will last for 4 months (months 1-4). The only study activity during the pre-intervention phase is the collection of routine PrEP uptake data to establish a baseline for PrEP prescribing at the GYN residency clinics and local PrEP clinics. Phase 2 is the implementation of the combined-care model at the LSU GYN residency clinic at UMCNO for 4 months (months 5-8). Phase 3 adds implementation of the social media campaign in the NOLA area for 4 months (months 9-12); implementation of the combined-care model at LSU GYN residency clinic at UMCNO will continue during this time (Figure 1). The layered approach allows for an opportunity to assess the effect of the combined-care model, and subsequently, to what extent the social media campaign additionally engages Black women and builds demand for PrEP.

We also include a comparator arm to evaluate changes in PrEP uptake due to other secular trends in the area and increases due to the social media campaign. The three comparator clinics are: (1) another GYN resident program (Tulane Downtown GYN Clinic), (2) the UMCNO PrEP clinic ([name], PI, is a provider), and the Tulane PrEP clinic.

5. Study Outcomes

We will assess both implementation outcomes (Table 1) and clinical outcomes (Table 2).

The implementation outcomes are guided by Proctor et al and include: acceptability, feasibility, appropriateness, adoption, fidelity, and maintenance.⁵ These outcomes will be assessed qualitatively through in-depth interviews (IDIs), debriefing sessions with GYN residents and leadership, medical chart reviews and/or de-identified Epic queries, training records, discussions with the BWAP Task Force, and social media metrics.

Table 1: Implementation Outcomes		
Outcomes	Measurement	Data sources & level of analysis
Acceptability	Satisfaction of complexity, content, relative advantage, and credibility of implementation strategies being delivered.	Provider: Debriefing sessions & IDIs Patient: IDIs Community stakeholders: Regular meeting with the BWAP Task Force
Feasibility	Fit from site perspective, suitability for everyday use, practicability.	Provider: Debriefing sessions & IDIs

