Appropriateness	Perceived fit and relevance to needs of Black cisgender women and suitability for GYN residents to implement	Provider: Debriefing sessions & IDIs Patient: IDIs Community stakeholders: Regular meeting with the BWAP Task Force
Adoption	
 • # residents trained/# residents rotating through GYN clinic • # residents initiating PrEP/# residents rotating through GYN clinic • Time between training providers & their beginning to implement 	Provider: Training records, chart review
Fidelity	
 • Time to implement: Average response time from social media inquiries by PrEP navigator • Completeness of combined care model delivery per eligible clients (% discussed PrEP; % provided PrEP counseling; % made a PrEP follow up plan; # monthly feedback sessions occurring) • Quality of implementation strategy delivery • Consistency of fidelity within and across providers 	Social media: Records of inquiries, calls and responses; metrics (e.g., post frequency, specific post reach, likes and amplification rates as a marker of quality) Provider: Epic data pull, chart review (completion/consistency); IDIs (quality) Patient: IDIs (quality)
Maintenance	
 • Adoption (see above) by providers over time • Fidelity of completeness (see above) of delivery over time 	Provider: Epic data pull, chart review
Reach	
 • # social media video views; # jingle plays; # campaign Facebook site visits 	Social media: Platform metrics (e.g. Facebook, TikTok)

Table 2: Clinical outcomes, primary and secondary	
Primary	
 • Total number of women overall and number of Black cisgender women initiating PrEP at the LSU GYN clinic during the pre-implementation period (Phase 1: months 1-4) compared to during the two implementation period phases (Phase 2: months 5-8 and Phase 3: months 9-12). • Comparison of the difference in patient numbers at the LSU GYN clinic during pre-implementation and the two implementation period phases with the difference in patient numbers during the same time frame at the Tulane GYN clinic. • Comparison of the difference in patient numbers at LSU GYN clinic and UMC PrEP clinic combined to the Tulane GYN and Tulane PrEP clinics combined during the same time frame to further investigate trends outside of the GYN clinics potentially impacted by the social media campaign.

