Secondary	
 • Proportion of PrEP-eligible women overall and Black cisgender women initiating PrEP at the LSU GYN clinic across the two implementation time periods (combined-care model only, Phase 2—months 5-8; combined care model plus social media company, Phase 3—months 9-12) • Proportion of women choosing follow-up care at the LSU GYN resident clinic versus transition to a local PrEP provider • Proportion of women initiating PrEP at the LSU resident GYN clinic who complete their first follow-up PrEP care visit (can only assess at the LSU GYN resident clinic or UMC PrEP clinic) • LDH navigator logs (number of contacts, number of appointments made through the PrEP navigator)

6. Data collection

Chart reviews, use of electronic medical records, and provider surveys

For baseline data collection (Phase 1, months 1-4), we will retrospectively collect data at the LSU GYN resident clinic, Tulane Downtown GYN Clinic, and the LSU PrEP clinic at the end of Phase 1 for the previous 4 months. Data will consist of the number of new PrEP prescriptions per month (overall among women and number of Black cisgender women specifically). No identifiable data will be collected. We may also collect baseline data for up to 12 months prior to Phase 2 initiation to compare trends over time.

Because the number of PrEP prescriptions among women at the Tulane Downtown GYN clinic and the Tulane PrEP clinic is extremely low, we will administer a survey to clinic leadership or another representative to gather the aggregate, de-identified data throughout implementation of this study. We will not access patient records at these sites. To collect data from the UMC PrEP clinic, in which [name] (study PI) is a provider, we will collect the de-identified data via provider survey if feasible (since numbers are also low), or if necessary, through patients' electronic medical records (EMR).

We will continue to collect data on PrEP prescriptions at the Tulane Downtown GYN Clinic, the Tulane PrEP clinic, and the LSU PrEP clinic until the end of Phase 3.

For data collection during the implementation phase (Phases 2 and 3, months 5-12) at the LSU GYN resident clinic, we will collect the number of new PrEP initiation counts for cisgender

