We will conduct monthly feedback sessions throughout the study (e.g., at the end of each month-long rotation) with the LSU GYN residents and leadership. The purpose is to discuss their experiences with implementing the *Start the Conversation* initiative and make adaptations to the combined-care model (e.g. adjustments, additions and/or subtractions of action steps) as needed. The residents will receive information regarding their fidelity during the end of month feedback session and will have an opportunity to provide suggestions of components to change, add, or subtract to increase feasibility and acceptability. Residents and leadership will be informed that we will use information discussed at these meetings for research purposes (e.g., describing adaptations made during research dissemination). We will also use Epic data pulls of extractable data elements as needed to inform components that may need adaptation (e.g. was a PrEP conversation initiated, were shared decision-making talking points used).

8. Data analysis

We will evaluate the primary clinical outcomes using a difference-in-differences approach⁶ to account for changes within time periods (pre- and post-implementation) and across sites (LSU versus Tulane). Poisson regression will be used to determine synergistic effects of the social media layering using weekly PrEP initiation counts, comparing uptake across implementation periods and sites and employing a product term to assess the impact of jointly implementing the combined-care model and social media campaign. We will analyze the secondary clinical outcomes using descriptive statistics.

We will use thematic analysis to analyze the qualitative data from the IDIs. Informed by the Proctor outcomes⁵ and the Consolidated Framework for Implementation Research,⁷ analysts will first develop a structural codebook based on predetermined topics explored during data collection. Next, content codes will be developed to capture emergent content. Transcripts will be coded by two or more analysts. Analysts will conduct inter-coder reliability assessments on approximately 25% of the transcripts; discrepancies will be resolved through discussion, codebooks will be updated as appropriate, and subsequent text will be recoded as needed.

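### The primary PrEP initiation counts have no women-seen denominator for LSU in Phase 1 or for Tulane, so a sustained, site-specific volume change would blur the size of the effect

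*Protocol*

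**What the plan says.** **Outcomes (Section 5, Table 2).** The first primary outcome is "Total number of women overall and number of Black cisgender women initiating PrEP at the LSU GYN clinic during the pre-implementation period", set against Phases 2 and 3. The second is "Comparison of the difference in patient numbers at the LSU GYN clinic during pre-implementation and the two implementation period phases", set against the same difference at the Tulane GYN clinic. The third repeats this for GYN and PrEP clinics combined. All three are numbers of women, not proportions or rates.

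**Data (Section 6).** For Phase 1: "Data will consist of the number of new PrEP prescriptions per month (overall among women and number of Black cisgender women specifically". For the comparator afterwards: "We will continue to collect data on PrEP prescriptions at the Tulane Downtown GYN Clinic" and at the two PrEP clinics, to the end of Phase 3. The Tulane figures come from a survey of clinic leadership or another representative: "We will not access patient records at these sites".

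**The one planned denominator (Table 2, secondary).** "Proportion of PrEP-eligible women overall and Black cisgender women initiating PrEP at the LSU GYN clinic across the two implementation time periods". It covers LSU in Phases 2 and 3 only.

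**Analysis (Section 8).** Difference-in-differences for the primary outcomes, and "Poisson regression will be used to determine synergistic effects of the social media layering using weekly PrEP initiation counts". No volume term is mentioned.

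**Purpose of the comparator (Section 4).** "We also include a comparator arm to evaluate changes in PrEP uptake due to other secular trends in the area", and to capture increases due to the campaign.

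**Planning figures (Section 6).** The LSU GYN clinic sees 60 to 80 patients per week, about 30 of them eligible and about 2 starting PrEP. Over 8 months this is put at 2,400 seen, about 1,000 eligible and around 70 starting.

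**The concern.** A count of initiations is the number of women seen multiplied by the share of them who start PrEP. The combined-care model acts on the share. If average volume at LSU in Phase 1 differs from that in Phases 2 and 3, part of the before-after difference reflects volume. If volume moves at one site and not the other, the LSU-versus-Tulane contrast carries that movement too. A proportional change shared by both sites cancels on the ratio scale of a Poisson model, so the point is made for changes specific to one site.

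The gap lies in the list of data items. An SAP, which may exist but is not at hand, could add an offset. It could not supply a Tulane denominator that the survey never asked for.

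**Working it through.** **Inputs.** From Section 6: 60 to 80 patients per week (midpoint 70), about 2 initiations per week and 2,400 women in 8 months. Calendar: 4 months = 4 × 365.25 / 12 / 7 = 17.39 weeks per phase, or 34.78 weeks for Phases 2 and 3. Assumptions, because the protocol gives no figure: 0 to 9 LSU initiations in Phase 1 at 70 women per week, and 1 to 5 Tulane initiations per phase (Section 6 says only that Tulane numbers are extremely low).

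**1. The plan's own figures.** At 34 weeks: 70 × 34 = 2,380 seen, 30 × 34 = 1,020 eligible, 2 × 34 = 68 starting. These reproduce 2,400, about 1,000 and around 70. The 2,400 total implies 2,400 / 34.78 = 69.0 women per week, so a steady volume near the midpoint.

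**2. Volume alone, Phase 1 to Phase 2, prescribing unchanged.** With B initiations at 70 per week, a sustained move from 60 to 80 adds B × (80 − 60) / 70:

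- B = 0: 0
- B = 5: 1.4
- B = 9: 2.6

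The expected rise at steady volume is 2 × 17.39 − B = 34.8, 29.8 and 25.8 respectively.

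**3. Volume on top of the expected rise, B = 9.** Rise = 34.78 × (Phase 2 volume / 70) − 9 × (Phase 1 volume / 70).

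| Phase 1 → Phase 2 volume per week | Phase 2 count | Phase 1 count | Rise |
|---|---|---|---|
| 70 → 70 | 34.8 | 9.0 | 25.8 |
| 60 → 80 | 39.7 | 7.7 | 32.0 |
| 80 → 60 | 29.8 | 10.3 | 19.5 |
| 65 → 75 | 37.3 | 8.4 | 28.9 |
| 75 → 65 | 32.3 | 9.6 | 22.7 |

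**4. Against chance.** The Poisson SD of the rise is √(34.8 + 9) = 6.6. The 60/80 shift moves the rise by about 6.2, or 6.2 / 6.6 = 0.94 SD. The 65/75 shift moves it by about 3.1, or 0.47 SD.

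**5. Ordinary weekly variation.** If weekly volume varied independently and uniformly over 60 to 80, its SD would be 20 / √12 = 5.77. The difference between two 17-week means would have SD 5.77 × √(2/17) = 1.98 per week. Even at the implementation rate in both phases that is 1.98 × (2/70) × 17.39 = 0.98 initiations, which is negligible. Only a sustained shift matters.

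**6. Tulane.** The same proportional shift on 1 to 5 initiations moves 1 × 20/70 = 0.3 to 5 × 20/70 = 1.4 initiations.

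**7. False signal, prescribing unchanged.** With an assumed 0.5 initiations per week at the lower volume and 17.33-week phases, a 60-to-80 shift gives expected counts of 8.7 and 11.6. An exact two-sided 5% conditional test on raw counts then rejects with probability 6.3%, against 2.9% with a volume offset. At 0.1 to 0.25 per week both stay below 5%.

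**The case against.** **Counts are a legitimate choice.** This is a pilot seeking initial indicators, and Section 4 asks whether the campaign builds demand. Higher attendance may be part of the campaign's effect, and a rate would remove it. This stands, and it is why the raw counts should remain primary.

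**The volume effect is small and no sustained shift is foreseen.** The 60 to 80 is a weekly range, and the 2,400 total implies about 69 per week throughout. This stands. The 60/80 case is an outer bound.

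**The data may be available anyway.** Phase 1 is collected retrospectively and Epic pulls are planned, so LSU volume is probably recoverable. The Tulane survey is not shown, and an aggregate total could be requested without record access. This holds for LSU. For Tulane it holds only if the question is asked. The optional 12-month baseline helps to show drift in counts, but it is not a denominator.

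**A stronger reading that the protocol does not support.** A reader might infer from the 60-to-80 range that volume could shift LSU counts by 39.7 − 29.8 = 9.9 initiations per phase. That figure applies the implementation rate of 2 per 70 to both phases, so it describes Phase 2 versus Phase 3, where the secondary proportion already gives a partial check. It does not describe Phase 1 versus Phase 2.

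**Conclusion.** The point holds in a limited form. The LSU Phase 1 versus Phase 2/3 comparison and the LSU GYN versus Tulane GYN contrast rest on raw counts. The protocol lists no women-seen figure for LSU in Phase 1 or for Tulane in any phase. A sustained, site-specific volume change would therefore be mixed with prescribing.

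Across the assumed LSU baseline of 0 to 9 per phase, even the extreme shift only blurs the size of the expected rise, by about one Poisson SD at most. The baseline matters. For a rise to 2 per week, a 60-to-80 shift accounts for ln(4/3) / ln(2/b) of the log rate ratio, where b is the weekly baseline: 10% at 0.1, 21% at 0.5 and 42% at 1 per week.

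It would be wrong to conclude that volume could reverse the rise, that counts are the wrong primary measure, or that LSU volume is beyond recovery. This is a cheap improvement and not a material flaw.

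**What to change.** - **Section 6, LSU.** Add the number of women seen at the LSU GYN clinic, overall and if available for Black women, to the Epic pull for Phases 1 to 3. Take it by week where possible, to match the weekly Poisson model in Section 8.
- **Section 6, Tulane.** Add one monthly aggregate item, women seen, to the existing Tulane GYN survey. No record access is needed.
- **Table 2 and Section 8.** Beside the raw counts, report the LSU phase comparison per 100 women seen, or use women seen as an offset in a sensitivity analysis. Report the LSU GYN versus Tulane GYN contrast per 100 women seen descriptively. Keep the raw counts as primary, and leave the combined-clinic contrast on counts.

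The cost is one Epic query, one survey item and a few words in three places. There are three limits. The rate removes any campaign effect that acts through attendance, so rate and count must be read together. Women seen is not the same as PrEP-eligible women, so a change in case mix stays mixed with prescribing. The sparse Tulane comparator is not cured.

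### The LSU GYN primary count is specified differently before and after implementation, with no committed common source, so a change in capture or definition could be read as part of the effect

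*Protocol*

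**What the plan says.** Section 5, Table 2, lists as the first primary clinical outcome the number of women initiating PrEP at the LSU GYN clinic in Phase 1 (months 1-4) against Phases 2 and 3 (months 5-8 and 9-12).

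Section 4 describes the Phase 1 activity as "collection of routine PrEP uptake data to establish a baseline for PrEP prescribing". For that phase Section 6 says "we will retrospectively collect data at the LSU GYN resident clinic", alongside two other clinics, and "Data will consist of the number of new PrEP prescriptions per month". It names no source for the LSU GYN baseline.

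A separate sentence in Section 6 opens "For data collection during the implementation phase (Phases 2 and 3, months 5-12) at the LSU GYN resident clinic" and specifies counts of new PrEP initiations, by date, race and provider, taken from provider notes. The next sentence adds Epic pulls from note templates that are to receive new extractable fields, as a source for primary and secondary outcomes. Tracking of EMR prescription data for all patients seen in the study period appears only as something the team *may* do.

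For the two Tulane clinics, "we will administer a survey to clinic leadership or another representative to gather the aggregate, de-identified data" and "We will not access patient records at these sites". No reporting interval is given for these surveys after Phase 1.

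Section 8 assigns the primary outcomes to a difference-in-differences analysis with no stated time unit. It adds a Poisson regression "using weekly PrEP initiation counts, comparing uptake across implementation periods and sites". The interaction of the two strategies is to be examined in that model by "employing a product term to assess the impact of jointly implementing the combined-care model and social media campaign".

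**The concern.** The two sides of a primary contrast are not described as the same measurement. Between baseline and follow-up at the same clinic, three things change in the text: the event (prescriptions, then initiations), the time resolution (monthly, then dated), and the source (none named, then provider notes and new templates).

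The new templates arrive with the intervention, and only at the treated clinic. If they capture more or fewer events than the baseline method, the difference is added to or subtracted from the apparent effect. Because it affects LSU only, subtracting the Tulane change does not remove it. An analysis plan written later cannot restore a common source that was never collected.

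A smaller question concerns time units: if the weekly Poisson model is meant to include Phase 1, monthly totals cannot be split into weeks.

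**Working it through.** **1. The plan's own volume.** Section 6 expects about 2 initiations per week. Eight calendar months are 34.8 weeks, and 2 × 34.8 = 69.6, which agrees with the stated figure of around 70. That is about 35 per four-month phase.

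**2. Assumptions.** The protocol gives no Phase 1 count and no capture rates. I assume:
- a true Phase 1 count B of 2 to 10;
- a Phase 1 source that captures s = 0.7 to 1.3 times what the later source captures;
- one Tulane GYN prescription per phase (the protocol says only that Tulane numbers are extremely low).

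**3. Effect on the LSU pre/post ratio.** Observed ratio = 35/(sB). The log shift is -ln(s): +0.357 at s = 0.7 and -0.262 at s = 1.3. The standard error of the log ratio is √(1/B + 1/35).

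| B | True ratio | Read at s = 0.7 | Read at s = 1.3 | SE | Shift/SE |
|---|---|---|---|---|---|
| 10 | 3.5 | 35/7 = 5.0 | 35/13 = 2.7 | 0.359 | +0.99, -0.73 |
| 2 | 17.5 | 35/1.4 = 25.0 | 35/2.6 = 13.5 | 0.727 | +0.49, -0.36 |

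**4. Effect on the difference-in-differences.** The log shift is unchanged, but the standard error becomes √(1/B + 1/35 + 1 + 1): 1.459 at B = 10 and 1.590 at B = 2. The shift is then 0.24 or 0.18 SE at B = 10, and 0.22 or 0.16 SE at B = 2. The sparse Tulane counts dominate the noise.

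**5. Could it produce a false signal?** As an illustration only, take no true change: Phase 1 ~ Poisson(sB), Phases 2-3 combined ~ Poisson(2B), and an exact conditional binomial test with p = 2/3 and 2.5% per tail. The protocol does not specify this test.

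| B | s = 1 | s = 0.7 | s = 1.3 |
|---|---|---|---|
| 10 | 3.1% | 8.2% | 8.7% |
| 5 | 2.5% | 3.8% | 5.2% |
| 2 | 1.1% | 0.5% | 2.6% |

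A clear excess over 5% appears only at the top of the assumed baseline range.

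**6. The Poisson model.** Take the two GYN clinics with illustrative phase counts of 5/35/35 at LSU and 1/1/2 at Tulane. With site and phase terms, a weekly grid and monthly totals with a log(weeks) offset give identical results:
- combined-care term: ln[(35/5)/(1/1)] = 1.946, SE √(1/35 + 1/5 + 1 + 1) = 1.493;
- product term: ln[(35/35)/(2/1)] = -0.693, SE √(1/35 + 1/35 + 1 + 1/2) = 1.248.

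The product term uses only Phases 2 and 3, so dropping Phase 1 leaves it unchanged. Without Phase 1, a combined-care main effect equals the site indicator (5 columns, rank 4); with Phase 1 the design has full rank (6 of 6).

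**The case against.** The strongest reply is that the source point rests on silence, not contradiction. The Section 6 subsection heading covers chart review, EMR and surveys for every phase. The optional EMR tracking could span the whole study, and its wording already links prescriptions to initiations. Section 6 also permits up to 12 months of data before Phase 2. This stands in part: the protocol nowhere says that the sources will differ. But the longer baseline names no source either, and an option is not a commitment when the follow-up source is spelled out.

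A reader might infer that the weekly Poisson model cannot be fitted to the baseline. The text does not support that as stated. Section 8 speaks of implementation periods, and Section 5 (Table 2) uses that term for Phases 2 and 3 and calls Phase 1 pre-implementation. On that reading no weekly baseline is needed, and the model's stated target, the product term, remains estimable. The aliasing of combined care with site is then no defect for that target, since the pre/post effect belongs to the difference-in-differences. If Phase 1 is included, an offset resolves the mismatch, and only week-level checks of baseline dispersion, trend and autocorrelation are lost.

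It is also fair to object that every magnitude above rests on assumed inputs, in a pilot that seeks initial indicators of effectiveness.

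**Conclusion.** The concern holds as a minor point. The protocol describes the LSU GYN primary count differently on the two sides of its first primary contrast and commits to no common source. A reader might infer that the pre/post comparison is biased; the documents do not show that. They leave open a risk of unknown size and direction, confined to the treated clinic and not removed by the Tulane comparison.

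Under the assumed inputs it could distort the size of the LSU ratio by up to about one standard error, but it is small against the noise in the difference-in-differences. It could not create the effect the study plans for; it would matter more if uptake fell well short of 2 per week. The time-unit question is secondary and conditional on Phase 1 entering the Poisson model.

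**What to change.** 1. In Section 6, change the EMR prescription tracking from *may* to *will*. Apply it as a full census, with one definition (a new PrEP prescription), to the LSU GYN clinic in Phases 1, 2 and 3, and use it for the primary count in every phase. Keep provider-note and template data for fidelity and secondary outcomes.
2. In Section 8, state whether the Poisson model includes Phase 1. If it does, use monthly counts for all clinics with a log(weeks) offset and overdispersion-adjusted standard errors. Weekly totals should not be requested from the Tulane clinics, whose very low counts would yield mostly zeros and single-person cells.

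The cost is a few sentences and a query that the protocol already contemplates; aggregate counts keep the Phase 1 promise of no identifiable data. There are two downsides. The primary count becomes prescriptions written, whereas Table 2 speaks of initiating PrEP, so its wording should be aligned. On monthly data, residual degrees of freedom for the two GYN clinics fall from 2 × 52 - 6 = 98 to 2 × 12 - 6 = 18, so overdispersion is estimated less precisely.
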